1.0 PROTOCOL SUMMARY

1.1 Protocol Synopsis

Study Title	Surfacer® System to Facilitate Access in Venous Occlusions
Protocol Number	BVT.Surfacer.17-01
Type and Phase	Pre-Market Investigational Device Exemption (IDE) Study
Number of Sites	Three sites will participate in the study initially, with up to 10 sites overall.
Device Name	Surfacer® Inside-Out® Access Catheter System
Indication for Use	The Surfacer® Inside-Out® Access Catheter System is intended to obtain central venous access to facilitate catheter insertion into the central venous system for patients with upper body venous occlusions or other conditions that preclude central venous access by conventional methods.
Device Description	The Surfacer® Inside-Out® Access Catheter System (Surfacer® System) is designed to facilitate entry and placement of central venous access catheters within the peripheral vasculature. The Surfacer® System is comprised of four components: a Workstation (Workstation Sheath) for percutaneous access to the femoral vein; a Delivery Instrument (Surfacer Device) which contains a Needle Wire and Needle Guide which is advanced to the supraclavicular space; an Exit Target which provides fluoroscopic guidance to mark the exit point; and an Exit (Peelable) Introducer which is introduced over the Needle Wire to access the central venous system. The Surfacer® System facilitates the entry and positioning of standard access catheters by establishing a transient passage across venous occlusions. Once the access is obtained and a catheter is in place, the Surfacer® System is removed.

Study Design	This is a prospective, single-arm, multi-center, study to demonstrate the safety and efficacy of the Surfacer® System.
Study Objectives	
This goal of this study is to demonstrate that the Surfacer® System, once in place, facilitates stable upper body central venous access that is suitable for any conventional catheter.
 
Safety will be evaluated based on the overall rate of acute complications using the study device as compared to historical rates of device/procedure related safety events using conventional CVA methods.
 
Efficacy will be evaluated by the rate of transient successful central venous accesses created by the study device.

Planned Study Duration and Number of Subjects	
Total study duration is anticipated to be approximately 12 months.
 
A total of 30 subjects is planned. 10 subjects will be enrolled initially. After review of safety data, enrollment is expected to continue to 30 subjects overall. Subjects will participate in the study as follows:
 
 • Screening/Baseline • Procedure (Surfacer System procedure and CVA catheter insertion) • Hospital Discharge • 7-days (+7) Post Procedure (assessments are to occur on Day 7, or as soon as possible thereafter)
Study Sites	A minimum of three (3) sites in the United States and Europe will participate, with a majority of the subjects being enrolled at US sites if feasible.

Primary Study Endpoints	
Primary Efficacy Endpoint:
 
 • Rate of safe insertion and patency of CVCs created across venous occlusions. 
Primary Safety Endpoints:
 
 • Acute device safety, defined as the absence of procedural complications (hemopericardium, hemothorax, pneumothorax, blood transfusion, resuscitation, emergency post-procedural intervention, transfer to an intensive care unit, and death) at discharge and 7 days post-procedure • Overall device and procedure related anticipated adverse events compared to historical safety data from CV placement procedures.
Secondary Study Endpoints	
Secondary Efficacy Endpoint
 
 • Surfacer System clinical utility use from insertion into the femoral vein to sub-clavicular exit assessed by the ability of the Surfacer System to facilitate central venous access placement 
Secondary Safety Endpoint
 
 • Technique conversion rate

Inclusion Criteria	
 1. Subjects are between 18-80 years of age. 2. Subjects have been referred for placement of central venous access catheter. 3. Subjects have limited or diminishing upper body venous access or pathology impeding standard access methods. 4. Subjects are willing and able to give written informed consent.
Exclusion Criteria	
 1. Subjects are contraindicated for Surfacer System use if one of the following are found (per the IFU): 
 a. Occlusion of the right femoral vein; b. Occlusion of the iliac vein; c. Occlusion of the inferior vena cava. 2. Subjects are contraindicated for central venous access based upon the treating physician's opinion and institutional standard of care. 3. Subject has acute thrombosis within any vessel (SVC, jugular, inferior vena cava (IVC), brachiocephalic and subclavian) planned be crossed by Surfacer System. 4. Subject has tortuous anatomy which precludes a straight line from femoral venous entry to subclavian exit. 5. Subject has been diagnosed with active pericarditis or endocarditis. 6. Subject has a known or suspected pericardial effusion. 7. Subject has a known or suspected aneurysm or ectasia of ascending aorta, innominate artery, or subclavian artery. 8. Subjects who are pregnant or of childbearing potential not taking adequate contraceptive measures or nursing during the study.

1.3 Schedule of Assessments

STUDY ASSESSMENTS WILL OCCUR AS FOLLOWS:

Assessments/Interval	Screening	Baseline	Intra-Procedural	Hospital Discharge	7 Days (+7) Post Procedure ⁷
Informed Consent	X				
Study Eligibility	X				
Medical History/Demographics	X				
Physical Exam including Vital Signs		X		X	X
TCVO Lesion Type Classification		X			
Procedural Complication Assessment			X	X	X
Study Device Performance			X		
Medications (Antithrombotic & Cardiovascular)		X		X	X
Clinical Laboratory Tests¹					
Pregnancy Test ²	X ²				
Creatinine		X			
Coagulation Profile (APTT/PT/INR)		X		X	
CRP		X		X	
LDH/ASAT/ALAT		X		X	
Fibrinogen/D-dimer		X		X	
Exams and Tests³					
AP and LAT Chest X-Ray or cine-fluoroscopy		X ⁴	X	X ⁵	
Ultrasound or Venous Duplex Venography		X			
ECG 12-lead		X			
TTE			Only If Cardiac Events	Only If Cardiac Events	
Contrast Angiography			X		
Fluoroscopy			X		
Cone Beam CT/cardiac echo/advanced imaging modalities ⁶			X		
Adverse Events			X	X	X
Protocol Deviations		X	X	X	X

¹ Laboratory tests must be completed no more than 72 hours prior to the procedure.

² Pregnancy test is not required if patient is male or of non child bearing potential.

³ Ultrasound or Venous Duplex Venography must be completed no more than 7 days prior to the Screening Visit. Other Screening/Baseline tests must be completed no more than 30 days prior to the Procedure.

⁴ AP and LAT chest X-ray or cine fluoroscopy will be performed prior to the index procedure to define the pattern of occlusions, to rule out acute thrombosis, and to detect pleural fluid and mediastinal widening.

⁵ Post-procedural AP and LAT chest X-ray or cine fluoroscopy will be performed, ideally assessed immediately after the index procedure is complete, to check the correct placement and position of the CVA Catheter tip, rule out pleuro-pulmonary damage (pneumothorax, hemothorax, etc.), and to detect pleural fluid and mediastinal widening. If the Investigator determines that additional imaging is clinically indicated at the time of discharge (same day or next day discharge), a chest x-ray may be obtained.

⁶Cone Beam CT, cardiac echo, or similar advanced imaging modalities to be performed in subjects with Type IV TCVO lesions, and Type III TCVO lesions suspected to be characterized by unusually tortuous vessels or otherwise challenging anatomy.

⁷A +7 day visit window has been provided to allow for outpatient clinic scheduling. However - this visit is to occur on Day 7, or as soon as possible thereafter.

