3.4 Contraindications

The Surfacer System is contraindicated for patients with an occlusion of the right femoral vein, iliac vein

or inferior vena cava, or acute thrombosis within a vessel to be crossed by the Surfacer System. Special precautions may be required for patients with coagulation disorders and patients on anti-coagulation therapy.

The Surfacer System is not intended for use in the coronary or cerebral vasculature.

This device is not to be used in the arterial system.

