6.3.2 Exclusion Criteria

1. Subjects are contraindicated for Surfacer System use if one of the following are found (per the IFU):
 - a. Occlusion of the right femoral vein;
 - b. Occlusion of the right iliac vein;
 - c. Occlusion of the inferior vena cava.
2. Subjects contraindicated for central venous access based upon the treating physician's opinion and institutional standard of care.
3. Subject has acute thrombosis within any vessel (SVC, jugular, inferior vena cava (IVC), brachiocephalic and subclavian) planned to be crossed by Surfacer System.
4. Subject has tortuous anatomy which precludes a straight line from femoral venous entry to subclavian exit.
5. Subject has been diagnosed with active pericarditis or endocarditis.
6. Subject has a known or suspected pericardial effusion.
7. Subject has a known or suspected aneurysm or ectasia of ascending aorta, innominate artery, or subclavian artery.

8. Subjects who are pregnant or of childbearing potential not taking adequate contraceptive measures or nursing during the study.

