7.2 Screening and Baseline Assessments

Screening and Baseline assessments will include the following:

- Inclusion and Exclusion Criteria

- Medical history with demographics
- Physical exam with vital signs
- TCVO Lesion Type Determination
- Medications (antithrombotic and cardiovascular)
- Pregnancy test (not required if patient is male or non-child bearing potential)
- Clinical laboratory tests including coagulation profile (APTT, PT, INR), CRP, LDH, ASAT, ALAT, fibrinogen, D-dimer
- Ultrasound or venous duplex venography of upper body veins (SVC, jugular, inferior vena cava (IVC), brachiocephalic and subclavian) to rule out acute thrombosis within a vein to be crossed by the Surfacer System
- AP and LAT chest x-ray or cine fluoroscopy will be performed prior to the procedure to define the pattern of occlusion and to rule out acute thrombosis
- 12-lead ECG

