7.4 Intra-Procedural Assessments

During the Surfacer System procedure, the following data will be collected:

- Continuous ECG monitoring
- Contrast angiography (venography) to confirm occlusions.
- Fluoroscopy will be performed to confirm catheter tip position (catheter tip position must be visible on fluoro).
- Cone beam CT, intracardial echo, or other advanced imaging guidance to verify placement. Investigator must be able to clearly identify the level of occlusion. With Type IV occlusions, the Investigator must be able to definitively identify the remnant of SVC; if this cannot be accomplished by angiography, the operator should not proceed without advanced imaging guidance such as cone beam CT or intracardiac echo. Advanced imaging should also be utilized for some Type III TCVO lesions characterized by unusually tortuous vessels or otherwise challenging anatomy.
- AP and LAT chest x ray or cine-fluoroscopy will be performed post procedure to check the correct placement and position of the CVA Catheter tip, rule out pleuro-pulmonary damage (pneumothorax, hemothorax, etc.), and to detect pleural fluid and mediastinal widening.
- TTE (optional, only if cardiac events)
- Study Device Performance
- Adverse Events
- Protocol Deviations

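### The scan that must rule out acute thrombosis is timed from the Screening Visit, so it has no stated maximum age when the device is used

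*Combined protocol and SAP*

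**What the plan says.** Section 1.3 has three timing rules for tests done before the procedure:

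- Footnote 3, first sentence, on the venous imaging: "Ultrasound or Venous Duplex Venography must be completed no more than 7 days prior to the Screening Visit".
- Footnote 3, second sentence: "Other Screening/Baseline tests must be completed no more than 30 days prior to the Procedure".
- Footnote 1: "Laboratory tests must be completed no more than 72 hours prior to the procedure".

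Section 7.2 gives the purpose of the ultrasound or duplex study: "to rule out acute thrombosis within a vein to be crossed by the Surfacer System". That finding is exclusion criterion 3 in Section 6.3.2 ("Subject has acute thrombosis within any vessel" that the device is planned to cross). Section 3.4 also lists it as a contraindication: "acute thrombosis within a vessel to be crossed by the Surfacer System".

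Two other imaging steps bear on the question. Footnote 4 calls for a chest X-ray or cine fluoroscopy before the procedure, among other things "to rule out acute thrombosis, and to detect pleural fluid and mediastinal widening". Section 7.4 lists, during the procedure, "Contrast angiography (venography) to confirm occlusions".

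The synopsis and Sections 6.2, 7.1, 7.2, 7.2.1 and 7.3 cover participation, consent, screening, screen failure and enrollment. None sets a maximum interval between Screening and Procedure, and none asks for a repeat scan.

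**The concern.** A test that clears a patient for device use should be current when the device is used. This one only has to be current at Screening. Acute thrombosis can develop between the scan and the procedure. Section 5.1 calls catheter-related vein thrombosis a recurrent problem with longer-term access devices, although the protocol gives no rate per day from which a risk could be calculated.

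At stake is patient safety and the reliability of an eligibility check. A subject could meet every written timing rule and still be treated on the basis of an old scan. A monitor would have no written limit against which to call that scan out of date.

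**Working it through.** The plan states no figure to reproduce. The check reads the timing rules together and adds intervals.

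**Step 1: what each test is timed from.**

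| Test | Limit | Timed from | Source |
|---|---|---|---|
| Laboratory tests | 72 hours | Procedure | Section 1.3, footnote 1 |
| Other screening/baseline tests, including chest X-ray or cine fluoroscopy | 30 days | Procedure | Section 1.3, footnote 3, second sentence |
| Ultrasound or duplex study | 7 days | Screening Visit | Section 1.3, footnote 3, first sentence |

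The second sentence of footnote 3 covers only the *other* tests, so its 30-day limit does not reach the ultrasound.

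**Step 2: oldest compliant scan.** Let g be the number of days from the Screening Visit to the procedure.

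Maximum scan age at device use = 7 + g days.

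The documents put no limit on g, so the maximum is not defined.

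**Step 3: illustrations.** These values of g are assumptions.

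| Assumed g (days) | Oldest scan as written | Oldest scan, 7-day window before the procedure | Excess allowed now |
|---|---|---|---|
| 3 | 7 + 3 = 10 | 7 | 3 |
| 14 | 7 + 14 = 21 | 7 | 14 |
| 30 | 7 + 30 = 37 | 7 | 30 |

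The excess always equals g.

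**Step 4: is g limited indirectly?** Only for some subjects, and by inference. The pregnancy test is ticked under Screening and sits under the laboratory heading that carries the 72-hour rule. Read strictly, that puts Screening within 3 days of the procedure for women of childbearing potential, and the oldest scan is then 10 days. Men and women not of childbearing potential need no pregnancy test, so no such limit applies to them.

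**Step 5: do the other checks close the gap?** The footnote 4 imaging may be a chest X-ray up to 30 days old. The venography during the procedure is listed for confirming occlusions, and no instruction to stop for acute thrombosis is attached to it. Section 7.2.1 lets the investigator declare a screen failure at any point up to enrollment, but no current scan is required that would prompt one.

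**The case against.** The strongest reply is that the footnote is being read too literally. The scan is ticked under Baseline, the column that also holds the laboratory tests due within 72 hours of the procedure. The synopsis names Screening/Baseline as one stage, and Section 7.2 gives one list for both. If the two happen together, g is at most 3 days for everyone and the scan is at most 10 days old. Alternatively, the 30-day rule may imply that Screening itself falls within 30 days of the procedure, which gives 37 days.

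Both readings are possible, but the text establishes neither. The schedule keeps Screening and Baseline in separate columns and allows the other tests to be up to 30 days old, so a single visit within 72 hours of the procedure is not required. The 30-day limit applies to other tests, not to the visit. The Baseline tick allows a later scan without requiring one.

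A second reply is that device use does not rest on the old scan alone. All subjects have contrast angiography during the procedure. Section 3.3 has a contrast bolus confirm the sheath position before the Surfacer Device goes in. D-dimer is measured within 72 hours of the procedure, and the contraindication still applies at the time of use. This is a fair point and lowers the practical risk. However, none of these steps is set up as a required, current check for acute thrombosis, and the protocol attaches no D-dimer threshold or imaging trigger.

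It is also fair that the Instructions for Use, which are not among the documents, may set an imaging window; that the protocol gives no clinical basis for 7 days over another interval; and that the wording may be a drafting slip for the procedure. A slip would need the same correction, because sites will follow the text as written.

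**Conclusion.** The concern holds. As written, a compliant ultrasound or duplex scan has no stated maximum age at device use: the limit is 7 + g days, with g unstated. The 10-, 21- and 37-day figures rest on assumed gaps of 3, 14 and 30 days. They are the oldest ages allowed, not expected ages, since a site may scan later and the true gap may be short. The 10-day figure is also the indirect limit for women of childbearing potential, if the pregnancy test is done at the Screening Visit under the 72-hour rule.

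The size of the clinical risk cannot be calculated from the documents. No endpoint, analysis set or sample size is affected. The footnote can be reconciled with the Baseline column and with consent coming first, so the point is not a contradiction, nor a scan before consent. The rule is explicit but tied to the wrong event, and it should be corrected because the scan guards a contraindication.

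**What to change.** In Section 1.3, footnote 3, replace the Screening Visit with the Procedure as the event from which the 7 days are counted, or use another window before the procedure chosen by the sponsor's clinical team. Add that the scan is repeated if the procedure is delayed beyond that window. Put the same rule in Section 7.2 beside the ultrasound item.

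With a 7-day window the oldest scan at device use is 7 days for every subject, whatever the Screening-to-Procedure gap, and a monitor can check it. The cost is one footnote edit, one matching line, and an occasional re-timed or repeat non-invasive scan among the 30 planned subjects when a procedure is delayed.

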2.0 INTRODUCTION AND BACKGROUND

2.1 Background

2.1.1. Central Venous Access

[figure not shown]
Central venous access (CVA) is one of the most commonly performed procedures in medicine, vital to many patients with acute and chronic illness. Indications for CVA include life-sustaining therapies such as hemodialysis, chemotherapy infusion, parenteral nutrition, hemodynamic monitoring and fluid management.^{i, ii}

Central Venous Access Devices (CVADs) have become a mainstay for patients requiring intravenous (IV) administration of medications and other therapies. In fact, more than 7 million CVADs are implanted every year in patients in the United States, whilst in Europe this number is reported to be 3.5 million constituting a population dependent upon on CVADs (Figure 1).^{iii, iv}

Obstruction or occlusion of CVADs due to venous thrombosis, with a reported frequency of up to 41%, is a serious problem in patients requiring repeated access or semi-permanent access. Chronic venous occlusions occur when thrombus forms around a catheter or pacing lead, and organizes into dense thrombus or fibrous tissue that permanently obliterates the vessel lumen. As a CVA is vital to the management of many chronic medical conditions, occlusion of the vein hosting the access becomes a life-threatening disease. Other risks include infection, pain, infiltration or extravasation.

Figure 1. Conditions treated with Central Venous Access

[figure not shown]
Clinical Condition – Treatment Population

2.1.2 Techniques for Central Venous Access

CVA is typically obtained by puncturing one of the four large upper body veins; the right or left internal jugular vein, or the right or left subclavian vein (**Figure 2**). A guidewire is introduced through the puncture needle and advanced into the central venous circulation. A plastic dilator is advanced antegrade over the wire to enlarge the channel, and then the catheter is advanced to the superior vena cava or right atrium. The tip of a CVAD is generally placed in either the lower third of the superior vena cava (SVC) or the caval atrial junction (**Figure 2**). Due to a blood-flow rate of approximately 2 liters per minute, infusates are rapidly hemodiluted and distributed in the central venous system.^{v, vi}

Figure 2. Adult CVAD insertion and tip sites^{vii}

Catheters are categorized into (i) non-tunneled catheters, (ii) tunneled catheters with anchoring cuff, (iii) implanted ports (iv) apheresis/dialysis catheters (tunneled and non-tunneled) and (v) PICC (peripherally inserted central catheter) (**Table 1**).^{vii} They may have single or multiple lumens and can be open-ended or valved. Multiple lumen catheters are advantageous in patients undergoing stem cell transplantation or chemotherapy whereby a number of agents and blood products require simultaneous infusion. Blood products may be administered concurrently with other drugs infused through a multi-bore catheter.

Table 1: Common types of CVADs^{vii}

[figure not shown]
[figure not shown]
[figure not shown]
			
Non-tunneled Catheters	Tunneled catheters	Peripherally inserted central catheters (PICCs)	Implanted ports

Also called subclavian, percutaneous, acute-care, or short-term catheters.
 
Typically used for days or weeks, for all types of IV therapy, to draw blood, and to monitor central venous pressure.
 
May be placed bedside or, if necessary, in an emergency setting without sedation
	
Designed for long-term use and frequent venous access.
 
Provides a more reliable IV access.
 
Used for extended courses of antibiotics, chemotherapy, and parenteral nutrition
 
Surgically inserted
	
Often used when a catheter will be needed for less than 6 months or when access to the jugular or subclavian vein is unavailable
 
Can be used for most IV therapies and to obtain blood samples in a variety of care settings from diverse patient populations
 
May be placed bedside or in an outpatient setting
	
Consists of 2 attached parts:
 
the catheter and portal body with reservoir
 
Long-term dwell capacity, requiring little maintenance when not in use.
 
Useful for cyclically infused therapies, such as chemotherapy
 
Blood draws may be done through the port
 
Surgically inserted

Table 2 summarizes the advantages and disadvantages for each of the catheter categories. An experienced member of the Hematology Oncology team should make the decision regarding which type of catheter is most appropriate at the outset of therapy, to avoid multiple catheterizations. The decision made is based on diagnosis, length and type of therapy, patient preference, and clinical status, availability of patent veins, operator experience and previous central venous access history. For example, if an allogeneic transplant is planned a double or triple lumen skin-tunneled catheter should be inserted at the outset to ensure adequate access throughout chemotherapy and the subsequent transplant.

Table 2: Advantages and disadvantages of different catheters for CVA^{viii}

Catheter type	Advantages	Disadvantages
Nontunneled catheters	Choice of sites Easy to insert and remove Multiple lumina available	Short-term use
Skin-tunneled catheters*	Lower infection rates than nontunneled Long-term use	More complex insertion and removal
Ports	No external catheter Cosmetically attractive Patient can swim/bathe as normal Low maintenance Long-term use Lower infection rates than skin-tunneled catheters	Surgical insertion and removal Less suitable for frequent repeated access
Apheresis/dialysis catheters Nontunneled (e.g. Vascath™ Kimal) Skin-tunneled	Permit high blood flow rates Easier to insert and remove Lower infection rates than nontunneled devices Long-term use Good for patients with poor peripheral access who require both PBSC harvest and transplant procedure	Large bore Require flushing with concentrated heparin (for example 5000 U/ml, according to manufacturer guidelines) solution to maintain patency. Flush solution must be withdrawn prior to use Short-term use Complex insertion and removal Best inserted via internal jugular or femoral routes Higher thrombosis rate particularly with polyurethane variety. Polyurethane variety required to infuse blood/platelets because has greater internal diameter than silicone variety Slower flow rates particularly in silicone/valved varieties Catheter longevity lower than with skin-tunneled devices Incidence of malposition greater than in other types of CVC
PICC	Easy to insert and remove Do not require platelet support or correction of clotting prior to insertion/removal	

[figure not shown]
